6. STUDY & TREATMENT PLAN

Study Design

The proposed study will implement a cluster randomized block design where staff are nested within sites. The community-based provider sites and jails will be grouped into homogeneous blocks and then randomly assigned into 2x2 design for each block. The forty-eights sites will be assigned to one of four study arms using a matching strategy within the blocks that groups four jail-clinic combination together prior to randomization. Each jail and CB treatment provider (or clinic) in these combinations will be treated as a site. For instance, if a jail has two post incarceration CB treatment providers (or clinics) in the trial, this will be 3 total sites (of the 48 sites). Within the matching block of 4 jail-clinic combinations, one jail-clinic combination will be randomized to an arm of the study. Twelve sites (that will consist of jails or post incarceration

CB treatment sites) will be assigned to each arm. The number of jails and post-incarceration sites per arm are expected to be balanced, with an anticipated 4 jails and 8 post-incarceration CB provider sites per arm.

Matching will be based on; a) number of clinic sites the jail will be including in the study (as part of the jail-clinic combination), population of the county where the jail is located, and whether or not the jail is currently providing MOUD to CJ population, and if so, what type of MOUD. The blocking procedure will reduce variability within treatment conditions and yield more precise estimates of treatment effects. This strategy will allow for the study team to examine the effects of High versus Low-Dose coaching and ECHO on MOUD use rates in large and small settings. In the study design, there will be a 12-month implementation period followed by 12 months to track sustainability. Data will be collected at baseline, 12 months and 24 months.

[figure not shown]
Intervention

There will be two “scaling-up practices” used in this study; NIATx Coaching and ECHO Clinical Mentoring. The study will look at combination of these two practices to create four intervention study arms;

- 1) High-Dose Coaching/ECHO,
- 2) Low-Dose Coaching/ECHO,
- 3) High-Dose Coaching/No ECHO, and
- 4) Low-Dose Coaching/No ECHO

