Low-Dose Coaching / No ECHO	
 • Key stakeholders attend an in-person Kick-Off Meeting with Study Team & Coaches • One-hour conference call with Executive Sponsor • Two-hour NIATx webinar training with Change Leader/Team • Three (one-hour) coaching calls at months 4, 8, and 12 with Change Leader/Team 	

Data Source

Table 2 shows a complete list of Measures, Sources, and Tool/Frequency. The Executive Sponsor, Change Leader and Change Team at each jail and community-based provider site will be asked to complete one or two of the three main surveys based on their role(s) within the study: Organizational Survey, Staff Survey, and Physician Survey. Site staff participants will be sent links to complete the survey(s) via REDCap. Each organizational site will receive a \$1000 stipend per year for two years once all organizational, physician, and staff surveys have been completed.

The trial has 4 study arms that will have staggered starts in order to have sufficient training resources for the trial. Each arm will have 12 organizations/sites with N=48 total.

Organizational Surveys & Data:

Organizational surveys will be completed by Executive Sponsor (or their designee) three times during the project (baseline, 12 months and 24 months). The baseline survey will be conducted by phone interview with all 48 sites. To increase survey completion rates for the organizational surveys, the research team at UW will conduct follow-up phone calls and e-mails with the Change Leaders at Week 1 of post-survey distribution to assure the survey receipt, then at Weeks 4 and 12-post survey distribution if surveys are not complete.

We will assess Organizational Traits, Client Traits, Staff Characteristics, and number of prescribers at the sites at three points during the study - at organizational baseline (baseline), at end of the intervention period (month 12) and at end of sustainability period (24 months) using a mix of organizational and administrative data.

Each survey will take approximately 45 minutes to complete. This will result in 48 unique staff participants at baseline, and 4 new people per round at post-intervention (m12) and post-sustainability (m24), assuming 10% turnover at each round. This will result in a total of 56 unique participants and 144 total surveys.

Staff Surveys & Data:

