The designated Executive Sponsor or the Change Leader at each site will manage staff member recruitment to construct a change team of up to a seven (7) member Change Team. Up to two of the team members will be physicians. Each member of the change team as well as the change leader will be asked to complete staff surveys at baseline, 12m, and 24ms for a total of 8 "staff" surveys per site. Information on the implementation process will be gathered from site staff members during surveys and interviews.

The full Staff Survey including Organizational Readiness for Implementing Change (ORIC), Organizational Climate-Stress, Attitudes toward MOUD and Program Sustainability, will be administered three times during the study (baseline, 12m, 24m). Each survey is expected to take approximately 20 minutes or less to complete. Staff completing the surveys will receive consent documents when they are sent the survey link via REDCap. To increase survey

completion rates for the Staff Surveys, the research team at UW will conduct follow-up phone calls and e-mails with the Change Leaders at Week 1 of post-survey distribution to assure the survey receipt, then at Weeks 4 and 12-post survey distribution if surveys are not complete. Each survey cycle, at months listed above, will include up to 384 people per cycle. The 384 staff will include up to 8 participants from the 48 sites and will include the Change Leader (supervisor/member of the leadership staff), and up to 7 team members part of the Change Team (CJ staff, prescribers, clinicians, nurses, counselors, social workers, etc). Since many of the same staff will likely complete surveys in successive cycles, 536 unique staff are expected for survey completion across all three cycles. The 536 unique people projected assumes 20% or 76 new people per round occurs post-intervention and post sustainability round. There will be a total of 1,152 surveys.

Physician Surveys & Data:

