For MOUD and implementation outcomes at 12 month and at 24 month, mixed-effects models (random effects of programs; fixed effects of treatment condition and time) will be used for data analysis. Mixed-effects models, also known as multilevel or hierarchical linear models, are suitable because MOUD patients are nested within programs. Using a multilevel modeling framework, separate models will be applied for the percentage of patients and clinicians using MOUD and their frequency of use (for patients only). Program covariates as well as variables showing noticeable changes between phases will be included in the models as covariates to properly and efficiently estimate the effects of coaching and ECHO. We will examine the coaching and ECHO effects at each time point using cross-sectional multilevel models and will also implement growth curve models across time that include the coaching (high vs. low) and ECHO (present vs. absent) effects, time (baseline, post intervention, follow-up), and interactions between the intervention and time factors, while controlling for relevant time-varying and time-constant covariates. The rates and frequency of MOUD use (by buprenorphine, methadone and injectable naltrexone) and clinical and implementation outcomes will be measured repeatedly for the same programs, and it is expected that these values will be correlated over time. Therefore, instead of assuming independence (i.e., zero correlation) or a compound symmetry covariance structure (i.e., a constant correlation regardless of the proximity of measurement time points), we will allow errors to be auto-correlated or Toeplitz-structured,⁸² denoted as AR(p) or TOEP(p), in the growth curve models. The best-fitting covariance structure will be determined based on heuristic model comparison criteria such as AIC and BIC.

Mediation analysis:

We will examine the mediating effects of organizational factors on MOUD use through: NIATx Fidelity, ECHO Fidelity, the Organizational Readiness for Implementing Change (ORIC), Program Sustainability Assessment, and the Organizational Climate (Stress) measure. These factors will be analyzed using mixed-effects models. Through a mediation analysis, we can estimate the direct (NIATx and ECHO) and indirect effects (Adoption - # of prescribers) of each implementation arm.

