We will test the mediation effect of each potential mediator at each time point as well as across time. The R package 'mediation,' will estimate the causal mediation effects, examine moderated mediation effects, and conduct sensitivity analysis.⁷⁰

Effectiveness analysis:

We will compare MOUD use and retention rates in the 4 different arms using hierarchical linear models, where arm membership is used as the treatment assignment. We will examine the distribution of this outcome measure and will implement an appropriate transformation or nonlinear link function when appropriate (e.g., logistic, Poisson, exponential). Monthly data collection of the Effectiveness as well as Reach (MOUD use) measures, allows for analysis after each stage of NIATx and ECHO.

Table 4: Initiation & Retention

	Data	Source
Initiation	
• # of clients initiated on MOUD• # on MOUD	Organizational Spread Sheet
Retention	
• # of injections• # of weeks on Buprenorphine (30-Day Discontinuation)• # of methadone doses	State Database

Qualitative Analysis:

The qualitative analysis will be conducted by project staff, supervised by the qualitative methodologist, who will ensure that proper and consistent interviewing and analysis techniques are used. Project staff will conduct the interviews, which will be audio recorded and transcribed verbatim. Interviews with leadership personnel will focus on organizational culture, including the organization's approach to making process changes, as well as motivations and expectations for working with justice-involved populations. Interviews with staff will focus on the staff's perspectives on their organizations' experiences with identifying and implementing process changes. Project staff will conduct a directed content analysis of these data. Qualitative data will be summarized and analyzed to detect patterns in individual and clinical approaches to change that have been successful. This description will enhance our understanding of how the NIATx and ECHO models work in criminal justice settings and criminally involved populations, promoting valuable insights that can be applied to future dissemination and implementation of evidence-based practices.

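### The models for the coaching and ECHO effects on MOUD use (Reach) admit covariates because they changed after randomisation, and do not exclude variables the interventions can move

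*Combined protocol and SAP*

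**What the plan says.** Section 10, under Intervention and Sustainability, sets out mixed-effects models for MOUD and implementation outcomes at 12 and 24 months, with separate models for the percentage of patients and of clinicians using MOUD. The covariate rule is: "Program covariates as well as variables showing noticeable changes between phases will be included in the models as covariates". Its stated purpose is proper and efficient estimation of the coaching and ECHO effects. The growth curve models are also fitted "while controlling for relevant time-varying and time-constant covariates". There is no covariate list, no definition of a noticeable change or a relevant covariate, and no limit on when a covariate is measured.

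Section 3 makes Reach the primary aim. Section 6 describes 12 months of implementation followed by 12 months of sustainability tracking.

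The mediation paragraph of Section 10 names as mediators of MOUD use "NIATx Fidelity, ECHO Fidelity, the Organizational Readiness for Implementing Change (ORIC), Program Sustainability Assessment, and the Organizational Climate (Stress) measure", and describes "indirect effects (Adoption - # of prescribers) of each implementation arm". Section 6 re-measures most of these after baseline. For the staff survey, which also contains the ORIC: "Organizational Climate-Stress, Attitudes toward MOUD and Program Sustainability, will be administered three times during the study (baseline, 12m, 24m". For prescribers: "We will assess Organizational Traits, Client Traits, Staff Characteristics, and number of prescribers at the sites at three points during the study".

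**The concern.** The rule selects covariates by how much they move once the trial is under way. A variable can move for two quite different reasons.

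- It may drift for reasons unrelated to arm, such as a changing client mix. Adjusting for that is harmless and may help precision.
- It may move because coaching or ECHO moved it. Adjusting for it then removes whatever part of the effect runs through it, so the model no longer estimates the total effect of the randomised strategy. If the variable also shares an unmeasured cause with MOUD use, for example local leadership or funding, adjustment can produce an apparent effect where there is none.

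The rule does not separate the two kinds. A successful intervention makes the second kind more likely to qualify, because readiness, sustainability and prescriber numbers are among the things the strategies are meant to improve. At stake is the interpretation of the primary-aim estimates.

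**Working it through.** **Text.** Four facts, set side by side, carry the point.

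1. The rule is mandatory in tone and sits in the models for the intervention effects (Section 10).
2. The phases are the implementation and sustainability periods (Sections 3 and 6), so a change between them arises after randomisation.
3. Readiness, stress, sustainability and prescriber numbers are re-measured after baseline (Section 6). Section 8 gives only two time points for some of these, but any two of baseline, 12 and 24 months include a post-baseline one.
4. No section excludes them from the effect models.

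**Plan figures.** The plan gives no figure for this bias. Its related figure is power of .85 or higher in Section 10. The inputs are 42 programs, d = 0.51, ICC 0.10 and 75 patients per program.

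- Site-mean variance = 0.10 + 0.90/75 = 0.112 (SD 0.335).
- Noncentrality = 42 × 0.51² / (4 × 0.112) = 24.4, which on 1 and 40 df gives power of about 0.998. This satisfies the stated floor without reproducing .85. Nothing below depends on it.

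**Illustration 1, mediation (assumed inputs).** Let coaching shift the covariate by s SD and let a share f of the effect run through it. The adjusted coaching coefficient is 0.51 × (1 − f).

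- f = 0.25: 0.51 × 0.75 = 0.38.
- f = 0.50: 0.51 × 0.50 = 0.26.

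The covariate's slope on the outcome must be b = f × 0.51/s, and b² cannot exceed 0.112.

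- At s = 1 and f = 0.50, b = 0.255 and b²/0.112 = 58%: one covariate would explain 58% of site-mean variance within arms.
- At s = 0.5 and f = 0.50, b = 0.51 and b² = 0.26, which is impossible. The largest mediated share there is 0.335 × 0.5/0.51 = 33%.

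**Illustration 2, no true effect (assumed inputs).** Let a shared cause explain a fraction r of both the covariate and the site-mean outcome. In a cross-sectional model, the expected spurious coaching coefficient is −0.335 × s × r.

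- s = 0.5: −0.05 (r = 30%) and −0.08 (r = 50%).
- s = 1: −0.03 (r = 10%), −0.10 (r = 30%) and −0.17 (r = 50%).
- s = 0 (equal drift): zero.

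The sign reverses if the shared cause acts on the two variables in opposite directions. Simulated rejection rates (%) of a nominal 5% test, for r = 10 / 30 / 50%:

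| Model | shift 0.5 SD | shift 1 SD |
|---|---|---|
| Cross-sectional, 42 programs | 5.2 / 7.6 / 13.4 | 5.8 / 14.3 / 35.9 |
| Same, baseline MOUD use added | 5.2 / 7.0 / 8.9 | 5.4 / 10.7 / 18.6 |
| Growth curve, coaching by 12 months | 4.8–5.2 / 5.4–5.7 / 7.2–9.6 | 4.6–6.0 / 7.0–8.3 / 16.8–18.9 |
| 16 jail-clinic combinations of 3 sites | 5.0–5.4 / 5.3–7.0 / 9.9–12.8 | 5.0–6.1 / 8.6–11.3 / 20.3–26.3 |

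Without the covariate, rejection is 4.5–5.8% throughout; with the covariate but no shift, the cross-sectional model gives 4.5–5.2%. Ranges cover different assumed correlations within programs or combinations. The growth curve runs used a random program intercept, not the autoregressive or Toeplitz errors the plan specifies.

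The last row follows the Section 6 design, "Within the matching block of 4 jail-clinic combinations, one jail-clinic combination will be randomized to an arm of the study", with 16 jails and 32 community organisations as in Section 10. Section 9 (3 jails and 9 organisations per arm) and the administrative-data text of Section 6 (24 jails, 24 providers) give other counts, so that row is one reading only.

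**The case against.** The strongest reply is that the argument rests on silence. No section says readiness, stress, sustainability, fidelity or prescriber numbers will be covariates in the Reach models. The plan gives them a mediation paragraph of their own, which suggests the authors separate effect estimation from pathway analysis. The covariate rule can be read as aimed at client-mix drift: client traits are re-measured, and Section 10 expects patient numbers to vary over time.

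Much of this stands. A reader might infer that the plan will adjust for its mediators; the documents do not support that, and only leave it open. But the rule is not limited to client mix, and a separate mediation analysis does not take the mediators out of the effect models.

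A second reply is that the four-arm comparison under Effectiveness analysis, "where arm membership is used as the treatment assignment", mentions no covariates and so offers a clean estimate. It is not described as unadjusted or as primary, so it does not displace the rule. How the models should be ranked is a separate question.

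A third reply is that the largest rates come from extreme inputs. That is correct. The 35.9% needs a 1 SD shift, a shared cause explaining half of both variables, a cross-sectional model and no baseline MOUD covariate.

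**Conclusion.** The point holds as a defect in the covariate rule, and should be fixed before analysis. As written, the rule can bring variables affected by the intervention into the models for the primary aim, and nothing in the plan prevents it. Bias follows only if a selected variable differs by arm because of the intervention and either lies on the path to MOUD use or shares an unmeasured cause with it.

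The size cannot be established from the documents, which give no covariate shifts, mediated shares or shared-cause strengths. Under the assumptions above, a 10% shared cause gives practically no error inflation, while the extreme settings give substantial inflation. The mediation figures are simply 0.51 × (1 − mediated share). A reader might take 0.26 or 35.9% as a forecast for this trial, or conclude that the coaching and ECHO estimates will be biased; neither is supported.

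**What to change.** - Delete from the effect models the clause that admits variables because they changed from one phase to another.
- Adjust the coaching and ECHO models only for a short list of pre-randomisation covariates fixed in advance, such as jail versus clinic and either the matched block or the matching factors. Using both is largely redundant, since the blocks are formed on the factors, and it uses scarce degrees of freedom. Sections 6 and 9 list different matching factors and must be reconciled before the factors are used.
- Add the site's baseline MOUD rate in the 12- and 24-month cross-sectional models. In the growth curve model baseline is already a time level.
- Allow a time-varying covariate only if it is named in advance and the intervention cannot affect it, for example calendar time, given the staggered starts.
- Use post-baseline readiness, stress, sustainability, fidelity and prescriber numbers only in the mediation analysis.
- Report any adjustment for changes between phases as a labelled sensitivity analysis.

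This takes SAP wording and a short covariate list, with no new data. The cost is some loss of analyst flexibility.

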Collecting physician attitudes toward MOUD will occur at months 0, 12, and 24. An average of two prescribers are anticipated per site. Each survey will take 15 minutes or less to complete. Staff completing the surveys will receive consent documents when they are sent the survey link via REDCap. To increase survey completion rates for the Physician Surveys, the research team at UW will conduct follow-up phone calls and e-mails with the physicians at Week 1 of post-survey distribution to assure the survey receipt, then at Weeks 4 and 12-post survey distribution if surveys are not complete. This will result in 96 unique prescriber participants at baseline, and 9 new people per round at post-intervention (m12) and post-sustainability (m24), assuming 10% turnover at each round. This will result in a total of 114 unique prescribers and 288 surveys (@ 96/cycle).

The grand total of organizational surveys, at n=144, staff surveys at n=1,152, physician surveys at n=288. TOTAL will be N=1,584.

Administrative & Site Aggregate Data:

Administrative Jail Data will be collected from all 24 jail sites once every year for two years. We anticipate the data will include de-identified screening, assessment and/or intake data, demographic information, date entered/exited jail, sentence and length, etc.

Administrative State Criminal Justice Data will be obtained from state databases for all states that have a jail/community-based provider participating in the study. De-identified data will be provided once every year for two years for the participating jail jurisdictions (e.g. in Wisconsin it is counties). Data may include arrest dates, arrest offenses, court outcomes, sentence and length, etc.

Health and Treatment Provider Data will be provided by all 24 community-based treatment providers once every year for two years. De-identified data for jail based referrals would include number of referrals to OUD care, number of referrals to behavioral therapy or counseling, dates/type of care, MOUD units received, Medicaid payment data, etc.

Monthly Tracking Data will be provided by all 48 jails/community-based treatment providers on a monthly basis via spreadsheet provided by study team. Captured data for the jails will include MOUD treatment data, number screened for OUD, number receiving MOUD, number of

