Initial exploratory analyses of MOUD initiation and use will assess standard summary statistics and examine graphical representations of the data and will compare baseline characteristics among the 48 participating programs in this study, including patient age, ethnicity, nature of SUD, criminal justice status, organizational readiness for change, and MOUD. Chi-square and t-tests will be used to test for statistically significant baseline differences. Descriptive statistics and figures will display the distribution of each analytic variable collected at each time point.

The rates and frequency of MOUD use (buprenorphine, methadone and injectable naltrexone) will be measured repeatedly, and these values will be correlated over time. Instead of assuming independence (i.e., zero correlation) or a compound symmetry covariance structure (i.e., a constant correlation regardless of the proximity of measurement time points), we will allow errors to be auto-correlated or Toeplitz-structured, denoted as AR(p) or TOEP(p), in growth curve models. The best-fitting covariance structure will be determined based on heuristic model comparison criteria such as AIC and BIC.

Intervention and Sustainability:

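### For the three-occasion growth models, the plan's AR(p)/TOEP(p) errors force equal variances and equal lag-1 correlations; an unstructured program-by-time covariance is a cheap improvement

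*Combined protocol and SAP*

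**What the plan says.** Section 6 (Study Design) sets three waves: "Data will be collected at baseline, 12 months and 24 months". Section 10 (Intervention and Sustainability) states that "mixed-effects models (random effects of programs; fixed effects of treatment condition and time) will be used for data analysis", and the growth curve models contain the coaching and ECHO factors with "time (baseline, post intervention, follow-up), and interactions between the intervention and time factors".

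On the errors, section 10 (Data Analysis Plan) says "we will allow errors to be auto-correlated or Toeplitz-structured, denoted as AR(p) or TOEP(p), in growth curve models", and the same intention is repeated under Intervention and Sustainability. The order p is not given. The choice is left to the trial data: "The best-fitting covariance structure will be determined based on heuristic model comparison criteria such as AIC and BIC". No unstructured or heterogeneous-variance form, robust standard error or small-sample degrees-of-freedom method is named.

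Two other statements limit the point. The plan also fits separate models by occasion: "We will examine the coaching and ECHO effects at each time point using cross-sectional multilevel models". A longer series exists for Reach: "Monthly Tracking Data will be provided by all 48 jails/community-based treatment providers on a monthly basis via spreadsheet provided by study team" (section 6, Administrative & Site Aggregate Data).

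**The concern.** With three occasions, the program-by-time covariance has six free values: three variances and three covariances. AR(p) and TOEP(p) as conventionally defined allow at most three: one variance, one covariance for adjacent occasions and one for baseline to month 24. They therefore assume that programs are equally spread before and after the intervention, and that baseline predicts month 12 exactly as well as month 12 predicts month 24. An implementation trial gives reason to doubt both. Sites may be starting MOUD or expanding it (section 5), and current provision is a matching factor (sections 6 and 9).

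If either assumption fails, the growth model's standard errors are wrong for particular contrasts. AIC/BIC cannot correct this, because every structure on the list shares the restriction. At stake is the calibration of the tests and intervals for coaching and ECHO, including the intervention-by-time terms that only the growth model supplies.

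**Working it through.** **The plan's own figure.** The plan gives no figure for covariance over time. Its one related figure, power of .85 or higher for coaching, is a single-time calculation: d/√((4/42)(0.10 + 0.90/75)) = 0.51/0.1033 = 4.94, which gives power 0.998 on 40 df. The stated floor is met and does not depend on this point.

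**Inputs.** From the documents: three occasions, 48 programs (42 after attrition), four arms, alpha 0.05 (taken as two-sided). Assumed: the SDs and correlations over time, which the documents do not give.

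**Step 1: identifiability.** Take one value per program per occasion. A stationary covariance then has three distinct entries (variance, lag 1, lag 2).

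| Structure | Parameters | Rank |
|---|---|---|
| Program intercept + AR(1) | 3 | 3 |
| Program intercept + TOEP(2) | 3 | 3 |
| Program intercept + AR(2) | 4 | 3 |
| Program intercept + TOEP(3) | 4 | 3 |
| Unstructured, no intercept | 6 | 6 |
| Unstructured + program intercept | 7 | 6 |

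The low orders are identified. The higher orders are redundant beside an intercept, but they describe no richer a covariance than TOEP(3) alone.

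**Step 2: unequal variances.** A common-variance model uses roughly the pooled SD, √(mean of the three variances). With r = pooled SD / true SD at an occasion, type I error is about 2Φ(−1.96r).

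| SDs (baseline:12:24) | Pooled SD | r at m12, m24 | Approx. type I at m12, m24 | Simulated |
|---|---|---|---|---|
| 1:1.5:1.5 | √(5.5/3) = 1.354 | 0.903, 0.903 | 7.7%, 7.7% | 7.8%, 8.3% |
| 1:2:2 | √(9/3) = 1.732 | 0.866, 0.866 | 9.0%, 9.0% | 10.2%, 8.8% |
| 1:2:2.5 | √(11.25/3) = 1.936 | 0.968, 0.775 | 5.8%, 12.9% | m24: 12.8% |
| 1.5:1:1 | √(4.25/3) = 1.190 | 1.190, 1.190 | 2.0%, 2.0% | 1.1%, 1.5% |

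The simulations chose between AR(1) and full TOEP by AIC. The rising-spread rows used 48 programs, correlations of .5-.7 and 1,500 runs. The falling-spread row used 42 programs, correlations of .6/.5 and 800 runs. In the same simulations, the change to month 24 had type I error of 3.5% under 1:1.5:1.5 and 2.3% under 1:2:2, which is mildly conservative.

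**Step 3: equal variances, unequal lag-1 correlations.** With unit variances, change from baseline to month 12 has variance 2(1 − ρ). Correlations of 0.3 then 0.8 pool to 0.55, so r = √(0.45/0.70) = 0.80 and type I error is about 11.6% (simulated 11.5%, 42 programs). For 0.4 then 0.7, r = √(0.45/0.60) = 0.87, giving about 9.0% (simulated ratio 0.86, 7.4%). With 0.3 then 0.8 and spread that also rises, the month-12 change contrast is not conservative either: about 9% for SDs 0.5:1:1 and 11% for 0.7:1:1.

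**Step 4: the unstructured alternative.** Across the 42-program scenarios (residual df 42 − 4 = 38), unstructured with t(38) gave type I error of 3.5-6.2%, with a simulation error of about 0.6-0.7 points. Its ratio of estimated to true SE was 0.985-0.997. If variances are in fact equal, power at noncentrality 3.0 is 83.2% on 38 df against 84.2% on 76 df. With z tests, type I error runs at about 4.5-6.8%, so small-sample df matter.

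**The case against.** Much of the case on the other side stands.

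- **Cross-sectional models.** They estimate each occasion's own variance and use no AR/TOEP errors, so the inflated single-time figures apply only to contrasts read from the growth model. But the plan does not rank the two analyses, and the intervention-by-time terms come only from the growth model.
- **Direction.** A reader might infer that the month-12 and month-24 standard errors are simply too small. The documents do not support that. A mix of providers and non-providers can mean wide baseline spread, and the requirement that every site implement or continue at least one medication (section 5) could narrow it later. The errors would then be too large.
- **Identifiability.** A reader might infer that the planned models cannot be fitted. AR(1) or TOEP(2) with a program intercept can. The redundancy at higher orders hardly touches fixed-effect standard errors, which depend on the fitted marginal covariance, and the information criteria penalise the surplus parameter.
- **Monthly data.** Section 10 notes that "Monthly data collection of the Effectiveness as well as Reach (MOUD use) measures, allows for analysis after each stage of NIATx and ECHO". On a monthly Reach series AR/TOEP is sensible and unstructured is not: 25 points would need 25 × 26/2 = 325 parameters. But the written growth model codes three times, and Table 2 lists prescriber adoption, readiness, climate and sustainability at three waves only.
- **Other flexibility.** The plan allows a transformation or nonlinear link, which deals with some variance tied to the mean. Random slopes would also relax equal variance, but none is specified.
- **Selection.** Choosing a covariance by AIC/BIC is common practice, and the effect of the selection itself was not quantified separately.
- **Cost.** A reader might take the unstructured form to be free. It is not: it needs more parameters, small-sample df and a fallback.

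**Conclusion.** The point holds in a limited, conditional form. For three-occasion growth models, every named candidate imposes one variance and one lag-1 correlation, and AIC/BIC cannot select a structure that is not on the list. That much follows from the text.

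The size of the harm rests on assumed SDs and correlations and on complete, balanced, Gaussian program-level data. Under rising spread, the affected month-12 and month-24 contrasts have type I error of about 8-13%; under 1:2:2.5 the excess is at month 24, and month 12 stays near 6%. Change contrasts are then mildly conservative, provided that the lag-1 correlations are equal. Under falling spread, single-time contrasts sit at about 1-2%. Under lag-1 correlations of 0.3 then 0.8, the month-12 change contrast is at about 11.5%. The redundancy of AR(2) or TOEP(3) beside an intercept is minor. The cross-sectional models, any monthly Reach model and the stated power figure are untouched. This is a cheap improvement worth making, not a flaw that invalidates the analysis.

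**What to change.** In section 10 (Data Analysis Plan, and Intervention and Sustainability), for outcomes modelled at baseline, month 12 and month 24:

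- Prespecify an unstructured program-by-time covariance, with no separate program intercept because the two together are not identified. Under a logistic or Poisson link, use unstructured program-by-time random effects instead.
- Use Kenward-Roger or Satterthwaite degrees of freedom where available.
- Name a fallback for non-convergence, such as heterogeneous Toeplitz.
- Remove the AIC/BIC selection for these models.
- Keep AR/TOEP for any model of the monthly Reach series, and say which outcomes are analysed monthly and which at three occasions.

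The cost is a few sentences and no new data. There are six covariance parameters instead of two or three, which is feasible with 42-48 programs, and about one point of power is lost if the variances are in fact equal.
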